## **STUDY SUMMARY**

Study Title	First Contact Physiotherapy in Primary Care (FRONTIER): A Realist Evaluation of effectiveness and costs	
Internal ref. no. (or short title)	FRONTIER	
Study Design	Realist Evaluation of clinical and cost-effectiveness of FCP	
Study Participants	Providers of First Contact Physiotherapy (FCP) service; Key stakeholders who influence or are influenced by FCP, including providers, commissioners, patients, clinicians, practice staff.	
Planned Study Period	Three years	
Research Question/Aim(s)	To evaluate 'First Contact Physiotherapy' in general practice for patients with MSKDs, and provide evidence for the adoption of appropriate service delivery models with potential to:  a) provide optimal patient management b) show meaningful patient benefit c) relieve GP workload pressure d) promote better use of healthcare resources e) positively impact on whole systems MSK practice	

## **FUNDING AND SUPPORT**

FUNDER(S)	This study is fully funded by NIHR Health	
	Services & Delivery Research	
FINANCIAL AND NON FINANCIAL SUPPORT £764,225		
GIVEN		
HOST Bristol, North Somerset & South		
	Gloucestershire CCG	

**KEY WORDS:** 

First Contact Physiotherapy; Primary Care; Musculoskeletal; Realist Methodology

## **STUDY FLOW CHART**

## Phase 1: UK-Wide Survey

• Identify key aspects of service provision

# Phase 2: Realist Synthesis & Consensus Exercise

• Establish initial set of realist programme theories

### Phase 3: Realist evaluation

• Validation of programme theories

# **Phase 4: Impact of Outputs**

 Work with key stakeholders throughout to determine best format and routes for dissemination

This application relates to Phase 3 of the research plan outlined above. Stages 1 and 2 have received UWE FREC approvals (HAS 18.07.204), and stage 4 will require UWE FREC in the future. This information is provided to understand the context of the FRONTIER research study.

### 1. Summary

Musculoskeletal Disorders (MSKDs) are the leading cause of disability in the UK. They account for 10.8m lost work days annually and consume a significant amount of the health budget (approximately £5billion per annum is spent by NHS England). In 2014 there were 340m GP consultations in England, an increase of almost 12% over five years; approximately one third related to MSKDs. Given the increasing demand for GP services, and current difficulties surrounding GP recruitment and retention, alternative implementable and affordable models of care are essential.

One service initiative that is gaining commissioning attention is First Contact Physiotherapy (FCP), whereby patients attending GP surgeries for MSKD are treated by experienced physiotherapy practitioners on a first point of access basis; thereby providing timely specialist advice and reducing demands on GP time. A national search conducted by the applicants (in December 2016), found 85 locations in England and further initiatives in Wales offering FCP, but considerable variation existed in the way in which it was both implemented (e.g. staff seniority, duration of sessions, staff availability) and funded (e.g. shared between practices (federated), NHS seconded or privately employed by GP surgery). Importantly our 2016 search also revealed two key delivery models that are being implemented: (1) some locations employ expert physiotherapists who deliver assessment and physiotherapeutic management with or without onward referral; (2) others employ advanced expert physiotherapists who have additional validated competencies that permit them to prescribe, inject, order/interpret investigations (e.g. imaging) and list for surgery.

Local audits of both FCP models generally indicate that they reduce GP appointments and requests for unnecessary investigations, improve patient satisfaction and incur cost savings, in comparison to standard GP led approaches. Further robust research is needed however to examine the diversity and complexity of FCP models across the UK and determine the impact of emerging FCP models on patient outcomes, costs and systems level impact on MSK services. This research will provide robust evidence by conducting a realist evaluation (a theory driven methodological approach, used to evaluate social programmes) of delivery models to identify how FCP works, for whom, under what circumstances, how and with what resource implications.

The research will be conducted in four work-packages (WP):

- 1. A UK-wide survey scoping exercise to identify key aspects of service provision. This will facilitate purposive sampling of delivery models (case studies) that will be subject to further in-depth investigation.
- A rapid realist review of identified aspects of service provision, derived from the scoping exercise, to
  establish the initial set of realist programme theories underpinning FCP models of care. This will be
  followed by a consensus exercise with key stakeholders to validate the programme theories, in terms
  of the resource-response mechanisms in various contexts (context-mechanism-outcome
  configurations).

- 3. In depth case study of three key delivery models (FCP; FCP with additional qualifications [FCPAQ], which for the purposes of this study is defined as the ability to prescribe and inject; and usual GP care), each at four different general practices (sites), using realist evaluation to examine outcomes. Data will be collected (quantitative and qualitative) on what works, for whom, how and in what circumstances, accounting for aspects of the context that have causal impact: (e.g. privately employed or federated, practice size, deprivation), and at what cost. Realist qualitative interviews will be conducted with five stakeholder groups involved in service provision across sites: (i) clinic receptionists; (ii) GPs; (iii) physiotherapists; (iv) patients; and (v) commissioners. Patients (n=580) attending with MSKD, will be followed for 6 months to track changes in pain and functioning using the SF36-Physical Component Summary (primary outcome measure), and compared across the care models. Secondary outcomes will include mental health, patient safety, time off work/change of work practices, health related quality of life and patient satisfaction, and will be collected with validated outcome measures. The scope of the economic evaluation will be informed by the realist programme theories to determine the costs and cost effectiveness given a range of associated processes, contexts, and outcomes.
- 4. An integrated evaluation of the outputs from the other work-packages. Focus groups with key stakeholders in years 1, 2 and 3 will determine the most appropriate format and dissemination route for information gained throughout the study. We will assess any impact this has had on practice in focus groups in subsequent years (i.e. year 2 focus group will reflect on the outputs from year 1 etc).

Results will be used to develop an evidence-informed commissioning pack to assist implementation decisions. Where possible we will present data relevant to outcomes based commissioning processes.

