### Work Package 3: Realist Evaluation with in depth case study approach

- i. Empirically test the validated "programme theories" arising from WP2 using a series of nationwide case studies at GP practice sites (N=24).
- ii. Collect longitudinal cohort data for six months from patients attending GP surgeries with MSKD to determine the impact of FCP on clinical outcomes, quality of life, return to work and service satisfaction.
- iii. Gather qualitative evidence from key stakeholders (patients, GPs, physiotherapists, commissioners, and reception staff) in the case study sites to understand better the barriers and facilitators to FCP and the impact FCP has on pathways and equitable access to care.
- iv. Analyse implications of models of FCP for healthcare resource utilisation and costs, from the NHS perspective, compared to usual (no FCP) care, and assess cost effectiveness.
- v. Identify patient management safety concerns associated with various FCP models.
- vi. Understand the education and development needs of physiotherapists and other service staff (e.g. reception staff) for optimum FCP functioning, given the evolving primary care workforce (macro-context).
- vii. Present findings regarding effectiveness and contextual factors to help NHS decision-makers commission services that are safe, effective and cost effective for their areas.

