
 
Population size served by practice
 
	
 
Patient pathway
 
	general practice	
Different service models	
 
Receptionist role
 
		

 
Appointment times
 
	
 
Practice staff aware of
 
		

 
Number of clinics
 
	and suggesting service		

 
Number of physiotherapists
 
	
 
Perception of the role of the
 
		

 
Appointment content
 
	GP/other staff members		

0	Training	Perception of the role of the
0	Patient pathway	physiotherapist
0	Funding	Frontline physiotherapists
		
 
Skills, banding, and
 

		competencies of
		physiotherapists
		
 
Cost of employing therapists
 

		at different bands
		Local/national training
		opportunities (e.g. prescribers
		course availability/funding)

Work package 3 will consist of a Realist Evaluation with in depth case study approach. We will empirically test the validated "programme theories" using a series of nationwide case studies (N=39). This will follow a mixed methods approach including longitudinal cohort data for six months from patients attending GP surgeries with MSKD to determine the impact of FCP on clinical outcomes, quality of life, return to work/change in working patterns, perceived safety and service satisfaction. We will also seek to understand the education and development needs given the evolving primary care workforce; and assess the healthcare resource utilisation and costs, from the NHS perspective, compared to usual (no FCP) care.

Qualitative evidence will be gathered from key stakeholders (patients, GPs, physiotherapists, commissioners, and reception staff) in the case study sites to understand better the barriers and facilitators to FCP and the impact it has on pathways and equitable access to care.

Work package 4 will consist of focus groups with key stakeholders within each year of the study, when information becomes available to disseminate. We will work with key stakeholders to determine the most appropriate dissemination formats and routes to dissemination to ensure maximum impact and utility for each stakeholder group. In focus groups in subsequent study years (2 and 3) we will explore how this information was used and any impact that was achieved (i.e. in year 2 we will explore the outcome from dissemination in year 1 etc.)

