### Case study sampling and recruitment

Sampling: We require 39 case study sites across the UK, representing key sampling criteria (e.g. geographical location) that are likely to impact on service delivery. Case study sites will be sub-categorised into three strands:

- i. FCP (n=13)
- ii. FCP has additional qualifications [FCPAQ] (i.e. non-medical prescribing, injecting) (n=13)
- iii. No FCP service is available, physiotherapy provision via a different pathway [PT] (n=13)

In order to achieve a wide geographical sample, case study sites will be selected from England, Wales, Scotland and Northern Ireland. Amongst these, we will also ensure a range of urban and rural environments are included, and a range of sample deprivation based on GP population postcode deprivation index.

We will also record the duration that the service has been established as embeddedness is likely to impact on service outcomes. These will not be selection criteria for the sampling matrix, but the impact of service duration will be explored qualitatively.

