### Sample size

The aim of this research is to determine that FCP is not substantially worse (non-inferiority analysis) than GP based practice. For the purpose of assay sensitivity, the study is designed as a three arm design which includes usual GP care, FCP and FCPAQ. This sample size computation also accounts for the similarities of patients within each GP centre and treats each GP centre as a cluster within which patients are nested.

Based on Bishop et al (36) a non-inferiority margin of 2 units in SF-36 scale, that is the standard practice is either superior or worse no more than by 2 unit is assumed. Previous research in MSKD, such as Angst et al. (45) has estimated a minimal clinically important difference from 4 points for the SF-36v.2 PCS subscale. The standard deviation of the difference between the SF-36 score between models are assumed to be 6.5 based on Salisbury et al (7). In a one sided 0.05 significance non inferior hypothesis test, to achieve 80% power, 132 subjects are required. To account for the hierarchical nature of the design, i.e. patients are nested within GP centres, this number should be inflated by the design effect.

The design effect for a cluster size of 14 and an intra cluster correlation coefficient (ICC) of 0.0075 (29) will be 1.09, requiring a total sample size to 145 per arm. After allowing for attrition of 20%, the total subjects required per arm is increased up to 181, making the total of at least 13 GP centres per arm, and a per practice sample size of approximately n=14.

It is suggested to randomise 13 GP centres to each physio model and recruit 14 patients with MSKD within each GP centre. In our pilot study, 814 patients consulted with MSKD over 6 months (practice population ~6200). Similar studies in primary care (7, 36) report estimates of 40% of consulting patients being eligible and consenting, we are confident in recruiting the required sample, enabling comparisons between sites and models.

In the analysis, GP centres are included as a random effects in a General Linear Mixed model to account for similarity of patients within each GP centre. The sample size computation was performed using a combination of nQuery 8 and SAS version 9.4 software.

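### The protocol gives three site counts for work package 3 (12, 24 and 39), and its only patient total, 580, is not what its sample-size calculation yields (543 to 546)

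*Protocol*

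**What the plan says.** The Protocol states the size of work package 3 in several places, all in current text:

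- **Section 1, Summary (work package 3):** three delivery models, "each at four different general practices (sites), using realist evaluation to examine outcomes". That is 3 x 4 = 12 sites. The same paragraph says "Patients (n=580) attending with MSKD, will be followed for 6 months".
- **Section 4.2, Work Package 3, objective i:** the programme theories will be tested "using a series of nationwide case studies at GP practice sites (N=24", that is, 24 sites.
- **Section 5.1, Methodological Concept:** the same testing is described "using a series of nationwide case studies (N=39", that is, 39 sites.
- **Section 5.3, Case study sampling and recruitment:** "We require 39 case study sites across the UK", split 13, 13 and 13 over the three strands.
- **Section 5.3, Sample size:** 132 subjects before clustering, 145 per arm after the design effect and 181 per arm after 20% attrition, "making the total of at least 13 GP centres per arm, and a per practice sample size of approximately n=14".

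The Sample size section gives no overall total, so 580 is the only patient total for this work package in the document.

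**The concern.** All of these statements describe the work package 3 case-study practices. Nothing presents them as stages or subsets of one another, and nothing says which section prevails.

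The number of practices and the number of patients are the recruitment targets. They are also the inputs to the non-inferiority power claim, and in a clustered design they are not interchangeable: the design effect in the Sample size section is specific to 14 patients per practice. A given patient total spread over fewer practices carries less information.

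At stake is whether the study can be judged to have met its target. Recruitment could reach 24 practices and satisfy a written objective while missing the sampling requirement by 15. It could also reach 546 patients, satisfy the Sample size section and miss the Summary's total by 34. A non-inferiority comparison with less power than stated is more likely to end inconclusively.

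**Working it through.** **Inputs, all from the Sample size section:** "a non-inferiority margin of 2 units in SF-36 scale"; SD 6.5; one-sided alpha 0.05; power 80%; ICC 0.0075; cluster size 14; attrition 20%. The true difference is taken as zero, which is an assumption, but it is the one that reproduces the plan's figure.

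**Step 1. Reproduce the plan's figure.**
- Unadjusted n per arm = 2 x [6.5 x (1.645 + 0.842) / 2]² = 130.6, so 131 by the normal approximation. The t-based calculation gives 132 (power 0.802), as stated.
- Design effect = 1 + (14 - 1) x 0.0075 = 1.0975, printed as 1.09.
- 132 x 1.0975 = 144.9, so 145 per arm, as stated.
- 145 / 0.8 = 181.25, printed as 181.
- 13 practices x 14 = 182 per arm.

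The calculation reproduces.

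**Step 2. Total implied.** 3 x 181 = 543 and 39 x 14 = 546. The Summary's 580 exceeds these by 37 (6.8%) and 34 (6.2%).

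**Step 3. Power of each combination.** Completers are 80% of those recruited. Effective n per arm = completers per arm / [1 + (m - 1) x 0.0075]. Power = Φ(2 / [6.5 x √(2 / effective n)] - 1.645). The cluster size m is taken first as completers per practice and then as recruited per practice, which gives the two values shown.

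| Sites | Patients | Recruited per site | Effective n per arm | Power |
|---|---|---|---|---|
| 39 | 546 | 14 | 135.3 / 132.7 | 81.2% / 80.5% |
| 39 | 580 | 14.9 | 143.0 / 140.1 | 83.1% / 82.4% |
| 24 | 580 | 24.2 | 136.0 / 131.8 | 81.4% / 80.3% |
| 24 | 546 | 22.8 | 129.0 / 125.2 | 79.6% / 78.5% |
| 24 | 336 | 14 | 83.2 / 81.6 | 63.3% / 62.6% |
| 12 | 580 | 48.3 | 120.6 / 114.1 | 77.2% / 75.2% |
| 12 | 168 | 14 | 41.6 / 40.8 | 40.5% / 39.9% |

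Worked line for the Summary's design:
- 580 / 12 = 48.3 recruited per site, so 38.7 completers per site and 154.7 per arm.
- Design effect = 1 + 37.7 x 0.0075 = 1.282, so effective n = 120.6.
- 2 / [6.5 x √(2 / 120.6)] = 2.389, and Φ(2.389 - 1.645) = 0.772.

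With m as completers, 12 sites would need about 54 patients each, or 648 in total, to reach 80%.

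**Step 4. Where 580 may come from.** The same inputs with a cluster size of 24 give a design effect of 1 + 23 x 0.0075 = 1.1725. Then 132 x 1.1725 = 154.8, 154.8 / 0.8 = 193.5 per arm, and x 3 = 580. (Rounding up at each step would give 582.) Since 580 / 24 = 24.2 patients per site, 580 fits a design of 24 practices with about 24 patients each.

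**The case against.** The strongest reply is that the working design is clear. The sampling section, the recruitment section (which asks for thirteen practices without the service) and the Sample size section all use 39 sites or 13 per arm. The qualitative sample of about 210 points the same way. One patient and four professionals per site make 5 x 39 = 195 at 39 sites, against 120 at 24 and 60 at 12. The outlying figures stand in an overview and a list of objectives, and the governing calculation is sound. At 39 sites, 580 patients would do no harm, since that is 14.9 per practice and 82 to 83% power. The section also words its figures as a minimum number of centres and an approximate number of patients, so 546 is derived and not printed.

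Most of this stands. It shows that 39 is very probably the intended site count, and it limits the repair to wording. It does not remove the contradiction, because the Summary and the objectives are current text. It helps least with the patient total, where the only printed figure is one the calculation does not produce.

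Two stronger readings are tempting, and the document does not support them:

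- **That 24 sites would miss 80% power.** This needs the 24 sites of the objectives combined with the 14 per practice of the Sample size section, a 336-patient design that the Protocol states nowhere. With the Summary's 580 patients, 24 sites give 80 to 81%.
- **That the sample-size arithmetic is wrong, or that its power should be restated as 79 to 80%.** The 1.09 and the 181 are rounding. The lower power appears only if the test uses degrees of freedom counted from practices (about 79% for 39 x 14), which the Protocol's calculation does not do.

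**Conclusion.** The protocol is wrong as written. Three incompatible site counts (12, 24 and 39) and a patient total of 580 cannot all hold beside a calculation that implies 543 to 546. The calculation itself reproduces, and 39 practices of 14 patients deliver the stated 80%.

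Of the designs the text suggests, the Summary's falls short: 12 sites with 580 patients give about 75 to 77%, a loss of roughly 3 to 5 percentage points. Twenty-four sites fall clearly short only at 14 per practice (about 63%).

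These figures rest on the plan's own SD, margin, ICC and attrition, a true difference of zero, equal practice sizes and the plan's design-effect approach. That 580 is left over from a 24-site design is an inference from the arithmetic; the document does not say so.

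**What to change.** State one design everywhere:

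1. **Section 1, Summary:** change four practices per model to 13, and 580 patients to about 546.
2. **Section 4.2, Work Package 3, objective i:** change 24 sites to 39.
3. **Section 5.3, Sample size:** say that 132 is per arm, and print the overall total (39 x 14 = 546). Keep the stated 80% power.

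If the sponsor does intend 580 patients or 24 sites, redo the Sample size section for that number of practices and patients per practice, and carry the result through the sampling and recruitment sections.

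Optional tidying: print the design effect as 1.0975, and round 181.25 up to 182, which 13 x 14 already gives.

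The cost is text corrections in three places. No patients or practices are needed beyond those the sampling and Sample size sections already require.

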### 2. Background Information

Musculoskeletal Disorders (MSKDs) are the leading cause of disability in the UK (5, 16); they account for approximately 30% of General Practice (GP) consultations with many patients repeatedly consulting due to non-resolution of their problem (9-10); low back pain (LBP) is the most burdensome of these conditions (5). The economic impact is vast: accounting for 30.8million lost work days annually (17); costing NHS England almost £5 billion per annum (18); and approximately £8.6 billion in personal independence payments in England, Scotland and Wales annually (19).

The volume of people with MSKDs is contributing to the significant financial and service delivery burden faced in primary care (11) with General Practice experiencing unprecedented workload pressure. In 2014 there were approximately 340 million GP consultations in England, an increase of almost 12% in five years – representing the single greatest rise in any NHS sector (9, 11). This is compounded by current recruitment and retention difficulties (12) which are likely to increase. Recent figures suggest that 13% of GPs under the age of 50, and 60% of those aged over 50 expect to leave their position within the next five years (13). The impact this is likely to have on patient care is substantial, and will inevitably affect waiting times, safety and levels of satisfaction, that are already causing concerns (14). Given the exponentially increasing demand, coupled with the difficulties associated with GP recruitment and retention (11-13), alternative models of care that are implementable with relative ease, timeliness and affordability are essential. The pressing need for appropriate management is recognised by many of the Clinical Commissioning Group (CCG) Sustainability and Transformation Partnerships, with primary care workforce initiatives representing an area of priority (25), and the area has been highlighted by the Primary Care Workforce Commission as requiring further evaluation and understanding (33).

By definition, GPs have an extensive knowledge of the initial and ongoing management of multiple conditions. However, evidence suggests there is considerable variability in GP treatment of MSKDs, with care being offered that is inconsistent with national guidelines, and an under use of cost-effective strategies (such as exercise and self-management) (29). Furthermore, data suggest that many referrals to secondary care orthopaedic and scanning services may be inappropriate, resulting in increased waiting times and the potential for delay in cases that do necessitate urgent attention (14). There is a growing belief that GPs may not be the most appropriate healthcare professionals to manage the MSKD population, given their limited specialist musculoskeletal training (8, 30). By contrast, there is emerging evidence that physiotherapist practitioners expert in MSKDs are effective in making diagnoses and in achieving successful clinical outcomes; demonstrate good levels of patient satisfaction; and save money on unnecessary referrals (31-32). However, given the complexity of patients who may present with MSKD alongside multi-morbidities, it is as yet unclear whether non-physician led assessment and examination may lead to sub-optimal management. To date there is no systematic review specific to this emerging model of FCP and much of the available evidence is based on single case report and local audit data. This is reflected in 'The future of primary care. Creating teams for tomorrow' report (33), which recommends further research in this area.

